6.1 Agent Administration

Treatment will be administered on an outpatient basis. Reported adverse events and potential risks are described in Section 10. Appropriate dose modifications are described in Section 7. No investigational or commercial agents or therapies other than those described below may be administered with the intent to treat the patient's malignancy.

Hu5F9-G4 (magrolimab) dose will be calculated using the actual body weight of the patient at enrollment, and the dose may remain constant throughout the study unless a greater than 10% change in weight is observed.

All study patients will start **Hu5F9-G4 (magrolimab)** priming dose at 1 mg/kg IV followed by 30 mg/kg IV once a week in the first 2 cycles on a 28-day cycle. In cycle 3 and subsequent cycles, study patients will receive 30 mg/kg IV every 2 weeks on a 28-day cycle (see Table 2 below).

Hu5F9-G4 (magrolimab) may interfere with the assessment of RBC phenotyping. Hu5F9-G4 (magrolimab) binds to CD47 on RBCs and can mask detection of antibodies to minor antigens to the patient's RBC and ABO/Rh phenotype, DAT and Ab screen.

NCI Protocol #: 10384

Version Date: September 5, 2023

Before Starting Hu5F9-G4 (magrolimab),

- The following assessments must be performed and resulted.
 - ABO/Rh type and screen,
 - Antibody Screen,
 - DAT
 - Extended RBC phenotyping including minor antigens such as CcDEe, Cw, MNSs, Kk, FyaFyb, and Jka Jkb
 - RBC genotyping must be performed if a patient received any RBC or whole blood transfusion within the previous 3 months (unless laboratory has availability for special techniques for performing phenotyping for patients with recent transfusion). This may be performed for all patients in lieu of an extended RBC phenotyping.
- Ensure that the patient is provided a Patient Information Card containing their pre-study blood typing.

Hemoglobin must be ≥ 9.0 g/dL within 24 hours prior to the first 2 doses of Hu5F9-G4 (magrolimab) infusion. If several hemoglobin tests are performed prior to Dose 1 and Dose 2, the closest to the infusion should be considered. RBC transfusions are allowed to meet the minimum hemoglobin requirement prior to the first 2 doses.

Please refer to [Section 7.1.4](#) for instructions for monitoring for anemia and anemia symptoms post-infusion.

Table 2: Dose De-escalation Schedule for Phase 1b

Dose De-escalation Schedule				
Dose Level	Premedications: Precautions	Dose		Cycle Length
		Hu5F9-G4 (Magrolimab)	Mogamulizumab	
Level 1 (starting dose level)	650-1,000 mg acetaminophen oral (PO) and 25 mg diphenhydramine (PO or IV) or a comparable regimen at least 15 minutes before the first two doses of Hu5F9-G4	1 mg/kg IV priming dose; Then 30 mg/kg IV weekly in Cycles 1 & 2 followed by Q2W \geq Cycle 3. Give before mogamulizumab.	1 mg/kg IV (weekly for cycle 1, then Q2W starting from cycle 2)	28 Days
Level -1	Same as level 1	1 mg/kg IV priming dose; Then 20 mg/kg IV weekly in Cycles 1 & 2, followed by Q2W \geq Cycle 3. Give before mogamulizumab.	1 mg/kg IV (weekly for cycle 1, then Q2W starting from cycle 2)	28 Days

Q2W = Every 2 weeks, IV = Intravenous
**Priming dose will be given one week before Cycle 1 over 3 hours (+/- 30 minutes)*
***Hu5F9-G4 (magrolimab) to be administered before mogamulizumab on days when both treatments are given*
**** Within 24 hours prior to each of the first 2 doses of Hu5F9-G4 infusion, patients must have a documented hemoglobin level of ≥ 9 g/dL. Patients who do not meet these criteria must be transfused and have their hemoglobin rechecked to meet the minimum hemoglobin threshold prior to administering each of the first 2 doses of Hu5F9-G4. An additional hemoglobin must be checked 3 to 6 hours after the initiation of the first and second doses of Hu5F9-G4. The patient should be transfused as clinically appropriate. Investigators should consider additional hemoglobin monitoring during the first week of treatment in patients with symptoms of anemia or at increased risk for complications of anemia.*

As of the July 2023 amendment, the phase 1b portion has been completed with an enrollment of 6 patients at dose level 1. Out of the 6 patients treated, 1 experienced a DLT. The recommended phase 2 dose (RP2D) has been established as dose level 1 (30mg/kg magrolimab starting cycle 1).

Table 3: Regimen Description for Phase 2 (Hu5F9-G4 (magrolimab) + Mogamulizumab Arm)

Regimen Description					
Agent	Premedication; Precautions	Dose	Route	Schedule	Cycle Length
Hu5F9-G4 (Magrolimab)	650-1,000 mg acetaminophen oral (PO) and 25 mg diphenhydramine (PO or IV) or a comparable regimen at least 15 minutes before the first two doses of Hu5F9-G4 (magrolimab).	1 mg/kg priming dose, then 30mg/kg per schedule	IV over 2 hours* and given before mogamulizumab **	1 mg/kg priming dose, then 30 mg/kg weekly for cycles 1-2, then Q2W starting from cycle 3	28 days (4 weeks)
Mogamulizumab	No additional premedications	1 mg/kg	IV	Weekly for cycle 1, then Q2W starting from cycle 2	

Q2W = Every 2 weeks, IV = Intravenous
**Priming dose will be given over 3 hours (+/- 30 minutes)*
***Hu5F9-G4 (magrolimab) to be administered before mogamulizumab on days when both treatments are given*
**** Within 24 hours prior to each of the first 2 doses of Hu5F9-G4 infusion, patients must have a documented hemoglobin level of ≥ 9 g/dL. Patients who do not meet these criteria must be transfused and have their hemoglobin rechecked to meet the minimum hemoglobin threshold prior to administering each of the first 2 doses of Hu5F9-G4. An additional hemoglobin must be checked 3 to 6 hours after the initiation of the first and second doses of Hu5F9-G4. The patient should be transfused as clinically appropriate. Investigators should consider additional hemoglobin monitoring during the first week of treatment in patients with symptoms of anemia or at increased risk for complications of anemia.*

Table 4: Regimen Description for Phase 2 (Mogamulizumab Only Arm)

Regimen Description					
Agent	Premedication; Precautions	Dose	Route	Schedule	Cycle Length
Mogamulizumab	650-1,000 mg acetaminophen oral (PO) and 25 mg diphenhydramine	1 mg/kg	IV	Weekly for cycle 1, then Q2W starting from cycle 2	28 days (4 weeks)

	(PO or IV) or a comparable regimen at least 15 minutes before the first dose of mogamulizumab.				
Q2W = Every 2 weeks, IV = Intravenous					

For patients who crossover to the Hu5F9-G4 (magrolimab)/mogamulizumab combination due to progression or lack of response after 6 months, no washout will be required and treatment will proceed with an identical schedule as the combination arm starting with the priming dose of Hu5F9-G4 (magrolimab).

6.1.1 CTEP IND Agent

6.1.1.1 Hu5F9-G4 (magrolimab)

All cohorts in both phase 1B and phase 2 portion will follow the same dosing schedule, though the dose of Hu5F9-G4 (magrolimab) may vary, following the de-escalation design of the phase 1B portion (see Table 2). For patients receiving the combination of Hu5F9-G4 (magrolimab) and mogamulizumab, treatment will start with a priming dose of Hu5F9-G4 (magrolimab) of 1mg/kg IV without mogamulizumab. Starting one week later, patients will receive the designated dose of Hu5F9-G4 (magrolimab) (either 30mg/kg or 20mg/kg IV) every week for eight weeks. After the first 8 weeks, the schedule of Hu5F9-G4 will change to every 2 weeks ongoing. Mogamulizumab treatment will also start one week after the priming dose of Hu5F9-G4 (magrolimab) at the FDA-approved dose and schedule.

6.1.2 Other Agent

6.1.2.1 Mogamulizumab

All cohorts in both phase 1B and phase 2 portion will follow the same dosing schedule. For patients receiving the combination of Hu5F9-G4 (magrolimab) and mogamulizumab, treatment will start with a priming dose of Hu5F9-G4 (magrolimab) of 1mg/kg IV without mogamulizumab. Mogamulizumab treatment will start one week after the priming dose of Hu5F9-G4 (magrolimab) at the FDA-approved dose and schedule of 1mg/kg IV every week for 4 weeks. After the first 4 weeks of weekly mogamulizumab, the mogamulizumab schedule will change to every 2 weeks ongoing.

6.2 Definition of Dose-Limiting Toxicity

DLT Definition: A DLT is defined as any Grade 3 or greater AE that is assessed as related to at least 1 study treatment that occurs during the DLT Assessment Period (DLT exceptions are defined below). The DLT period during the phase 1 study will be 4 weeks from the first infusion of Hu5F9-G4 (magrolimab) (priming infusion). To be assessable for a DLT, patients must have

NCI Protocol #: 10384

Version Date: September 5, 2023

received at least three infusions of Hu5F9-G4 (magrolimab), two infusions of mogamulizumab, and completed four weeks of assessment, or else have experienced a DLT anytime after receiving the priming dose of Hu5F9-G4 (magrolimab). Patients unable to receive the planned treatment during the four weeks due to treatment-related adverse events will also be considered to have experienced a DLT.

DLT Exceptions: The following are exceptions to the DLT definition and will NOT be considered a DLT:

- Grade 3 anemia; however, Grade 3 hemolytic anemia is considered a DLT.
- Grade 3 hyperbilirubinemia that resolves to \leq Grade 2 with supportive care within 1 week and is not associated with other clinically significant consequences.
- Transient Grade 3 nausea, vomiting, diarrhea, local reactions, influenza-like symptoms, myalgias, fever, headache, acute pain, or skin toxicity that resolves to \leq Grade 2 within \leq 72 hours after medical management (e.g., supportive care, including immunosuppressant treatment) has been initiated.
- Grade 3 fatigue that resolves to \leq Grade 2 within 1 week on study.
- Grade 3 magrolimab-related infusion reactions in the absence of an optimal pretreatment regimen, which is defined as acetaminophen or a comparable non-steroidal anti-inflammatory agent, plus an antihistamine and corticosteroids.
- Grade 3 electrolyte disturbances (hyperkalemia, hypophosphatemia, hyperuricemia, etc.) that resolves to \leq Grade 2 or baseline within 1 week.
- Grade 3 or 4 lymphopenia or grade 3 leukopenia not associated with other clinically significant consequences.
- Transient (\leq 48 hours) Grade 3 fatigue, local reactions, flu-like symptoms, fever, headache, nausea, emesis, and diarrhea.
- Other single laboratory values out of normal range that have no clinical correlate, and resolve to Grade \leq 1 or to baseline within 7 days with adequate medical management.
- Tumor flare phenomenon defined as local pain, irritation, or rash localized at sites of known or suspected tumor.
- Grade 3 rash, erythroderma, skin pain or photosensitivity that resolves to \leq Grade 2 within 1 week with adequate medical management. Grade 4 rash or any grade Stevens-Johnson syndrome or toxic epidermal necrolysis will be considered DLTs.

Management and dose modifications associated with the above adverse events are outlined in Section 7.

Dose de-escalation will proceed within each cohort according to the following scheme (Figure 7) (Hong *et al.*, 2019). Dose-limiting toxicity (DLT) is defined above.

[figure not shown]

Figure 7: Phase 1b Dose De-escalation Design

Six patients will be enrolled at dose level 1 of 30mg/kg Hu5F9-G4 (magrolimab) and 1mg/kg mogamulizumab. If ≤ 1 DLT is observed in the initial 6 patients, then dose level 1 will be selected as the RP2D. If 2 DLTs are observed in the initial 6 patients, then an additional group of 3 patients will be enrolled at dose level 1. If there are no DLTs in this 3 patient group, then dose level 1 will be selected as the RP2D. If at any point there are >2 DLTs seen at dose level 1, then this dose level will close, and 6 patients will be enrolled at the new dose level -1: 20mg/kg Hu5F9-G4 (magrolimab) and 1mg/kg mogamulizumab. If ≤ 1 DLT is observed in the initial 6 patients, then dose level -1 will be selected as the RP2D. If 2 DLTs are observed in the initial 6 patients, then an additional group of 3 patients will be enrolled at dose level -1. If at any point there are >2 DLTs seen at dose level -1, then the trial will be stopped for unacceptable toxicity. It is believed that further reductions below a dose of 20mg/kg would not achieve adequate target occupancy for Hu5F9-G4 (magrolimab).

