6.3 General Concomitant Medication and Supportive Care Guidelines

Because there is a potential for interaction of Hu5F9-G4 (magrolimab) and mogamulizumab with other concomitantly administered drugs, the case report form must capture the concurrent use of all other drugs, over-the-counter medications, or alternative therapies. The Principal Investigator should be alerted if the patient is taking any agent known to affect or with the potential for drug interactions. The study team should check a frequently-updated medical reference for a list of drugs to avoid or minimize use of. Corticosteroids may interfere with accurate disease response assessment. High potency topical corticosteroids and systemic corticosteroids doses greater than 10mg prednisone daily or its equivalent are prohibited unless needed to treat adverse events. Effort should be made to taper steroids to the minimum required dose. Other anti-lymphoma therapies are prohibited including retinoic acids and phototherapy. Appendix C (Patient Clinical Trial Wallet Card) should be provided to patients if available.

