7.1 Safety Management Guidelines

7.1.1 Management of Infusion-related Reactions

The most common adverse events associated with IRRs include chills, pyrexia, back pain, nausea, vomiting, hypotension, dyspnea, and headache. These primarily occur with the first two doses of Hu5F9-G4 (magrolimab) (1 mg/kg), and are mostly observed during the infusion or several hours afterward.

Preventive Measures

Premedication should include oral acetaminophen and an antihistamine (IV or oral) before the initial doses of Hu5F9-G4 (magrolimab) or in the case of re-priming of Hu5F9-G4 (magrolimab). Premedication is required prior to the administration of the intial doses of Hu5F9-G4 (magrolimab). Refer to Section 6.1 Agent Administration.

Management of IRRs

- For grade 1 IRRs, described as mild transient reaction, infusion interruption is not indicated, intervention is not indicated:
 - Remain at bedside and monitor patient until recovery from symptoms.
- For grade 2 IRRs, infusion interruption is indicated, but patient responds promptly to symptomatic treatment (e.g., antihistamines, non-steroidal anti-inflammatory drugs, narcotics, corticosteroids, IV fluids); and prophylactic medications are indicated for ≤ 24 hours:
 - Stop the Hu5F9-G4 (magrolimab) infusion, begin an intravenous (IV) infusion of normal saline, and consider treating the patient with diphenhydramine 50 mg IV (or equivalent) and/or 500–750 mg oral acetaminophen.
 - Remain at bedside and monitor patient until resolution of symptoms.
 - Corticosteroid therapy may also be given at the discretion of the Investigator.
 - If the infusion is interrupted, wait until symptoms resolve, then restart the infusion at 50% of the original infusion rate.
 - If no further complications occur after 1 hour (± 10 minutes), the rate may be increased to 100% of the original infusion rate. Monitor the patient closely.
 - If symptoms recur, stop infusion and disconnect patient from the infusion apparatus. No further Hu5F9-G4 (magrolimab) will be administered at that visit.

- Premedications should be considered before any future infusions.
- The amount of Hu5F9-G4 (magrolimab) infused must be recorded on the case report form (eCRF).
- Patients who experience a grade 2 IRR during the post-infusion observation period that does not resolve during that time should be observed until the AE resolves, with vital sign measurements as medically indicated for the management of the AE.

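### The between-arm toxicity comparison by default leaves out a first Grade 3 magrolimab infusion reaction but counts mogamulizumab reactions, so it leans slightly toward not triggering

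*Combined protocol and SAP*

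**What the plan says.** Section 6.2 defines a DLT as a related Grade 3 or higher AE in the assessment period, then lists exceptions. One covers "Grade 3 magrolimab-related infusion reactions in the absence of an optimal pretreatment regimen". The optimal regimen is acetaminophen or a comparable anti-inflammatory, "plus an antihistamine and corticosteroids". The exception names magrolimab only. The same section also counts as DLTs "Patients unable to receive the planned treatment during the four weeks due to treatment-related adverse events".

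The specified premedication is steroid-free:
- **Doublet arm.** Section 6.1 (Table 3), Section 7.1.1 and Section 8.1.1 call for acetaminophen plus an antihistamine, or something comparable, before the early magrolimab doses.
- **Control arm.** Table 4 specifies the same two drugs "or a comparable regimen at least 15 minutes before the first dose of mogamulizumab".
- **After a Grade 3 reaction.** Only then does Section 7.1.1 recommend IV dexamethasone, for the next two doses.

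Magrolimab is "to be administered before mogamulizumab on days when both treatments are given", so on shared days a doublet-arm reaction has to be attributed to one drug, the other or both.

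Section 9.1 (Interim Safety Analysis) uses the DLT criteria twice in Phase 2. A single-arm rule holds accrual if the first-course DLT rate on the combination exceeds 30%. A between-arm comparison of AEs meeting DLT criteria, at any time on treatment, convenes the Toxicity Monitoring Committee.

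**The concern.** An exemption of this kind makes sense in dose-finding, where one would not de-escalate for a reaction that steroids might have prevented. In the randomized comparison the same criteria do a different job: they are meant to show whether adding magrolimab adds toxicity. Infusion reaction is one of two risks that Section 2.2.1.2.2 identifies for magrolimab. Section 10.1 lists it as likely (>20%) for magrolimab and less likely (<=20%) for mogamulizumab. A comparison that by default omits the first Grade 3 event of this type for the added drug, and keeps it for the backbone drug, leans toward not triggering.

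Section 6.3 gives a reason for avoiding steroids: "Corticosteroids may interfere with accurate disease response assessment". That explains the premedication. It does not explain counting the two drugs' reactions differently.

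At stake is the count of patients who have a Grade 3 magrolimab reaction and then continue treatment.

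**Working it through.** **Inputs (Section 9.1).** One-sided type I error 0.15, with 0.044 spent at 28 patients (14 per arm) and the remainder at 56 (28 per arm). Control rate 41%, doublet rate 62%, stated trigger probability above 70%. Worked triggers: 5/14 vs 10/14 and 11/28 vs 16/28.

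**Boundaries.** z1 = 1.706 from 0.044. With correlation sqrt(0.5) between looks, the remaining error gives z2 = 1.095.

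**The protocol's own figures.** The two-look normal approximation gives 70.8% (unpooled variance) or 69.5% (pooled), which agrees with the stated figure. Exact binomial enumeration with the pooled z gives 67.1%; its trigger probability at 41% on both arms is 14.2%. Exact values are used below. Both worked examples trigger: z = 1.895 > 1.706 and z = 1.337 > 1.095.

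**Assumed rate r of exempt Grade 3 reactions.** The documents give none. The nearest figure is in Section 2.2.1.2.2: 21 serious magrolimab-related infusion reactions among 401 patients, 21/401 = 5.2 events per 100 patients. Serious is not Grade 3 and events are not patients, so this does not fix r. I take 2% and 5%, which is 28 × r = 0.6 and 1.4 doublet patients at the second look.

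| Reading of 62% | Doublet rate compared with 62% | r = 2% | r = 5% |
|---|---|---|---|
| Counted rate, as Section 9.1 words it; exempt reactions then added, independent overlap | 1 − 0.38(1 − r) = 62.8%, 63.9% | 67% → 69% | 67% → 72% |
| Already includes them; exempt reactions then removed, independent overlap | 1 − 0.38/(1 − r) = 61.2%, 60.0% | 67% → 65% | 67% → 61% |
| Already includes them; these patients have no other DLT-level AE | 0.62 − r = 60%, 57% | 67% → 61% | 67% → 53% |

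**Effect of one patient.** Suppose one doublet patient in each worked example had an exempt reaction as the only qualifying event. Then 5/14 vs 9/14 gives z = 1.51 < 1.706, and 11/28 vs 15/28 gives z = 1.07 < 1.095. Neither triggers. Both examples sit at the boundary, so this shows that single patients can matter there; it says nothing about how often that happens.

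**The case against.** The strongest objection is that the exemption may catch little. Section 7.1.1 orders the infusion stopped at once for a Grade 3 reaction, and says reactions occur mainly with the first two magrolimab doses, inside the four-week window. The clause on being unable to receive planned treatment could then make many of them DLTs. This stands in part: the text does not say which provision prevails, and the table assumes the clause catches none. If it caught half (an assumption), r = 5% would become 5% × 0.5 = 2.5%, close to the 2% column.

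Second, the asymmetry is by drug, not by arm. A reaction attributed to mogamulizumab counts on either arm. Section 6.2 also exempts transient fever, flu-like symptoms, headache and skin toxicity whatever the drug, so some control-arm reactions may drop out too. This stands; it would be wrong to infer that every control reaction counts and every doublet reaction does not.

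Third, the stated trigger probability is not wrong. Section 9.1 words 62% as the rate of AEs meeting the criteria, so it already excludes exempt reactions. The 41% equals the Grade 3-4 AE rate quoted from the earlier phase 3 trial (75 of 184), so the scenario is illustrative.

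A reader might also infer that the 30% hold rule is compromised and that the six Phase 1b patients should be recounted. The documents do not support that. The rule is single-arm, so there is no between-arm bias, and exempting reactions without steroid premedication is a defensible DLT choice there. Counting everything has a price: starting from 1 of 6 and checking after each of 41 doublet patients, at a true first-course rate of 25% the chance of an accrual hold is 49%, against 32% if reactions at r = 5% (independent overlap) are exempt. Nothing in the documents says that a Phase 1b patient had such a reaction.

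**Conclusion.** The point holds for the between-arm comparison, and it is minor. By default a first Grade 3 magrolimab infusion reaction does not enter it, while Grade 3 mogamulizumab reactions do unless another exception fits. The direction follows from the text; the size rests on an assumed Grade 3 rate and on the clause catching none of these reactions.

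On the protocol's wording of 62%, counting them adds about 2 to 5 percentage points to the trigger probability. If 62% includes them, the exemption costs about 2 to 6 points with independent overlap and 6 to 15 with none. A rate of 10% would give larger losses, down to 38% with no overlap, but nothing in the documents supports a rate that high.

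A reader might infer that these reactions go unseen. They do not. A Grade 3 reaction exceeds the Grade 2 limit for exemption from expedited reporting (Section 10.1). Grade 4 reactions, and Grade 3 reactions despite steroid premedication, are outside the exemption. The treatment-related death trigger and the trigger for stopping before the third cycle do not use the DLT definition. The Data Coordinating Center, the DSMC and the DSMB also review the trial (Sections 9.1, 9.6 and 14).

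**What to change.** Add one sentence to Section 9.1: for the between-arm comparison of AEs meeting DLT criteria, every Grade 3 or higher infusion reaction related to either study drug counts, on both arms, whatever premedication was given. For this comparison, that also settles whether the clause on missed treatment overrides the exemption, and removes the dependence on which antibody is blamed on shared infusion days.

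Leave unchanged the 30% hold rule, the Phase 1b count, the RP2D and the steroid-free premedication.

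The cost is small. AE grade and attribution are already collected, and no procedures or patients are added. The Toxicity Monitoring Committee may be convened somewhat more often; a trigger calls for its review and does not by itself stop accrual.
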